# **Important Instructions for Using This Protocol Template:**

- Add this completed protocol template to your study in CATS IRB (http://irb.psu.edu) on the "Basic Information" page, item 7.
- This template is provided to help investigators prepare a protocol that includes the necessary information needed by the IRB to determine whether a study meets all applicable criteria for approval.
- Type your protocol responses below the gray instructional boxes of guidance language. If the section or item is not applicable, indicate not applicable.
- For research being conducted at Penn State Hershey or by Penn State Hershey researchers only, delete the instructional boxes from the final version of the protocol prior to upload to CATS IRB (http://irb.psu.edu). For all other research, do not delete the instructional boxes from the final version of the protocol.
- When making revisions to this protocol as requested by the IRB, please follow the instructions outlined in the Study Submission Guide available in the Help Center in CATS IRB (http://irb.psu.edu) for using track changes.

# If you need help...

# 1.0 Objectives

# 1.1 Study Objectives

The overall goal of this study is to investigate the impact of orthostatic stress on cognitive function in postural tachycardia syndrome (POTS), and to assess the prevalence of Hypermobile Ehlers-Danlos Syndrome (hEDS) and Hypermobility spectrum disorders (HSD) in patients with POTS. **This study will be performed in a large cohort (100 POTS patients) at the Dysautonomia International Conference in Nashville, TN June 22-24, 2018**. Healthy control subjects will be enrolled at Penn State Hershey Medical Center. The central hypothesis is that active standing in POTS worsens cognitive function and related to joint hypermobility. We will test this hypothesis in the following two specific aims:

Aim 1: Determine impact of orthostatic stress on cognition in POTS. Hypothesis 1: Active standing in POTS worsens cognitive function. Cognitive function will be assessed in the supine and standing postures using a short battery of cognitive tests. These tests examine aspects of cognition known to be impaired in POTS patients including executive function (Stroop word color test), attention (CogState Identification test), and working memory (CogState two-back test). Aim 1 will be performed in POTS patients and in healthy subjects.

Aim 2: Determine the prevalence hEDS and HSD in POTS. We will assess patients for hEDS and HSD using a questionnaire and physical exam based on the new guidelines. Aim 2 will only be performed in POTS patients.

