### 4.1 Identification of subjects

- POTS patients will be recruited from attendees at the 2018 Dysautonomia International Patient Conference in Nashville, TN June 22-24, 2018. Announcements calling for participation will be made during the conference.
- Healthy control subjects will be recruited using Penn State Study Finder and a paper flyer.

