### 5.0 Consent Process and Documentation

#### **5.1** Consent Process

# **5.1.1 Obtaining Informed Consent**

#### **5.1.1.1** Timing and Location of Consent

Interested participants will report to the study room at the conference or at Penn State Hershey Medical Center CRC. They will be asked the screening questions. If eligible, study personal will obtain informed consent in all subjects. All subjects will be given sufficient time to read the consent, all procedures will be explain in layman's terms and they will be given a copy of the signed consent form.

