#### 8.3 Statistical methods

We will compare cognitive testing results by position using Wilcoxon signed-rank tests. Results will be compared between groups (POTS, controls) using Mann-Whitney U test.

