# 16.2 Feasibility of recruiting the required number of subjects

The Dysautonomia International Patient conference has 500 attendees which are mostly POTS patients and caregivers. In past years, over 100 participants have volunteered for the research study conducted at the conference. We expect to recruit and approximately 100 POTS patients at the conference. We expect to recruit 5-10 healthy subjects per month.

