# 17.0 Multi-Site Research

Not applicable.

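### Every POTS patient is tested at the Nashville conference and every control at Hershey, so the planned between-group test of raw cognitive scores cannot separate POTS from site and setting

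*Combined protocol and SAP*

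**What the plan says.** Section 1.1 places the patient cohort "at the Dysautonomia International Conference in Nashville, TN June 22-24, 2018", and section 4.1 gives no other source of patients: "POTS patients will be recruited from attendees at the 2018 Dysautonomia International Patient Conference in Nashville, TN June 22-24, 2018". Section 2.3 assigns the later mechanistic work at the home institution to a separate IRB protocol.

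For controls, section 1.1 says "Healthy control subjects will be enrolled at Penn State Hershey Medical Center", and section 4.1 adds "Healthy control subjects will be recruited using Penn State Study Finder and a paper flyer". Section 5.1.1.1 shows the two settings side by side: "Interested participants will report to the study room at the conference or at Penn State Hershey Medical Center CRC". Section 16.1 confirms that Hershey sessions take place in the clinical research center. Section 16.2 expects 5-10 healthy subjects per month.

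Cognitive test scores are among the primary endpoints (section 1.2). Section 8.3 compares positions by Wilcoxon signed-rank test and then says: "Results will be compared between groups (POTS, controls) using Mann-Whitney U test". It does not say whether the results compared are scores at one posture or changes between postures. No bridging sample, matching, standardisation across sites or covariate adjustment is described.

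**The concern.** Neither site contains both groups. Any difference between the conference room and the research center that affects test performance goes straight into the POTS-control contrast. Adjusting for site afterwards cannot help, because there is no within-site contrast to estimate from.

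The outcomes could plausibly respond to setting. Under section 7.2 the Stroop answers are spoken and recorded by a team member, and the Identification test is scored on reaction time. A group difference on a primary endpoint could then be reported as an effect of POTS when part or all of it came from where and when the subjects were tested. A setting effect in the opposite direction could equally hide a real difference. Controls do not enter Aim 2 (section 1.1) or complete the questionnaires (section 7.3), so the cognitive comparison is the main use of their data.

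**Working it through.** The plan has no power figure to reproduce. Section 8.2 describes a convenience sample and gives no significance level, effect size or SD.

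**Overlap, from the documents**

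- Planned controls at the conference: 0 of 50. Planned patients at Hershey: 0 of 100.
- Control accrual: 50 / 10 per month = 5 months; 50 / 5 per month = 10 months. Patients take 3 days.
- Controls expected in any 3-day window, with 30.4 days per month: 5 x 3 / 30.4 = 0.49 to 10 x 3 / 30.4 = 0.99. At most about one control would be tested in the same three days as the patients.

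**Illustration on raw scores**

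Assumptions: normal scores with SD 1, two-sided 5% test, 100 versus 50, no true POTS effect, and a site shift of d SD at both postures. The Mann-Whitney rejection rate is approximately Φ(d√0.955 / √(1/50 + 1/100) − 1.96), where √(1/50 + 1/100) = 0.173 and 0.955 is the efficiency of the test relative to the t-test under normality. The formula omits the negligible opposite tail.

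| d (assumed) | Formula | Simulation |
|---|---|---|
| 0.1 | 8% | 9% |
| 0.2 | 20% | 20% |
| 0.3 | 39% | 39% |
| 0.5 | 81% | 80% |

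For d = 0.2: 0.2 x 0.977 / 0.173 = 1.13, and Φ(1.13 − 1.96) = 0.20.

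**The same test on standing-minus-supine change**

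- Shift equal in both postures: it cancels within each subject, and simulated rejection stays near 5%.
- Shift at standing only, with an assumed supine-standing correlation of 0.7: the SD of the change is √(2 x (1 − 0.7)) = 0.775. Shifts of 0.1, 0.2 and 0.3 SD become 0.13, 0.26 and 0.39 SD of the change. Simulated rejection is about 11%, 30% and 58%.

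**What a bridging sample could deliver**

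Assume 25 of the 50 controls were tested at the conference (t-test power, two-sided 5%, difference 0.5 SD):

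- Conference versus Hershey controls, 25 versus 25: power about 41%. The 95% half-width is 1.96 x √(1/25 + 1/25) = 0.55 SD.
- POTS versus conference controls only, 100 versus 25: power about 60%, against about 82% for 100 versus 50.
- Conference time for the 30-minute orthostatic step: 100 x 0.5 h = 50 bed-hours for patients. Adding 25 controls costs 12.5 bed-hours; adding all 50 costs 25.

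**The case against.** The strongest reply is that the stated hypothesis does not need the controls. Hypothesis 1 is that standing worsens cognition in POTS, section 7.1 sets up a repeated-measures design, and section 8.3 tests posture by signed-rank. Each patient is compared with himself or herself at one site, and Aim 2 is confined to patients. This stands: neither analysis is touched by the aliasing of group with site.

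It is also fair that the rejection rates above show only what an assumed shift would do. They are not evidence that a shift exists. The documents say nothing about noise, fatigue or time pressure at the conference, and a shift common to both postures would vanish from a change score.

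Three stronger readings are tempting but not supported:

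- A reader might infer that operators differ between sites. Section 7.2 says only that a research team member records the Stroop, and section 16.5 describes one study team. Operator confounding is possible, not shown.
- A reader might infer that all controls follow the conference. Section 16.2 gives a rate, but no start date for controls is stated.
- A reader might take the entry "Not applicable" under Multi-Site Research as a decision to disregard site effects. It is a field in an IRB template, gives no reasoning about the analysis, and should carry no weight here.

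What remains is the between-group test itself. The plan names it, applies it to a primary endpoint, leaves its outcome undefined and states no limitation.

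**Conclusion.** The point holds for the POTS-control comparison of scores at a single posture. Aliasing with site and setting is complete by design. Aliasing with calendar period is near complete in practice, with at most about one control expected in any three-day window at the stated rate. The 20% to 80% range rests on assumed shifts of 0.2 to 0.5 SD and normal scores, and illustrates how sensitive the test is, not how large the bias is.

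A change-score comparison is more defensible but not immune. It assumes that any site effect is the same supine and standing; if that fails, the figures of 11% to 58% for standing-only shifts of 0.1 to 0.3 SD show what remains, given the assumed correlation of 0.7. It would be wrong to conclude that Aim 1 as a whole is uninterpretable, because the within-patient test of Hypothesis 1 survives.

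**What to change.** 1. In section 8.3, define the POTS-control comparison as a Mann-Whitney test on each subject's standing-minus-supine change. State that this removes a site effect only where it is equal in both postures. The contrast also addresses something the within-patient test alone cannot: whether standing affects patients more than healthy people.
2. In section 8.3, state that group differences at a single posture are descriptive and cannot be separated from site, and that Hypothesis 1 rests on the within-patient comparison.
3. In section 7.2, specify the same tablets, Stroop cards and testing script at both sites, and the same operators where possible. Record operator and site for every session.

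The cost is wording, some extra record-keeping and slightly narrower conclusions.

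Optionally, if conference capacity allows, test some healthy companions there as a bridging sample. Section 16.2 suggests a source: "The Dysautonomia International Patient conference has 500 attendees which are mostly POTS patients and caregivers". Apply the same health criteria as for other controls, and record age and any blood relationship to a patient. This is a trade-off rather than a clear gain. It takes conference bed time, companions may be related to patients or older than them, and recording this does not remove the bias. The number who would qualify is not stated, and 25 versus 25 controls would leave a site effect of 0.5 SD more likely missed than found.

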# 1.2 Primary Study Endpoints

Our primary endpoints are the scores on the cognitive tests and the Beighton score.

# 1.3 Secondary Study Endpoints

Our secondary study endpoints are questionnaire answers and blood pressure and heart rate during standing.

# 2.0 Background

#### 2.1 Scientific Background and Gaps

#### 2.2 Previous Data

POTS is a form of chronic orthostatic intolerance that produces daily symptoms such as fatigue, lightheadedness, palpitations, dyspnea, and nausea. POTS is defined by the presence of these symptoms along with an increase in heart rate of at least 30 beats/minute in adults within 10 minutes of standing. It is estimated that 1 to 3 million Americans have POTS and it predominantly effects women of childbearing age.

#### **Cognition in POTS**

Cognitive impairment or "brain fog" is experienced by almost all POTS patients and affects daily life including school and work performance. While most symptoms of POTS have an onset with orthostasis, it is unclear whether "brain fog" is posturally related. In my previous study, over 95% of POTS patients reported cognitive impairment, with many experiencing symptoms on a daily basis and even while supine. However, there is limited objective data to support this claim, with few studies evaluating cognitive function in POTS. To date, only five studies have objectively measured cognition in POTS. Working memory is the only cognitive domain that has been evaluated in the supine posture in POTS, and these studies found no impairments in working memory in POTS patients while supine. Multiple domains of cognitive function have been evaluated in POTS patients while seated and during head-up tilt (HUT). While seated, one study showed that POTS patients have clinically meaningful impairment in selective attention, cognitive processing speed, and executive function with no differences in psychomotor speed, memory function, or verbal fluency compared to age-matched healthy participants. During graded HUT, studies have demonstrated impaired attention, processing, and working memory in POTS patients compared to healthy participants. Therefore, evidence suggests that POTS patients

have impaired cognition even while seated, when tachycardia and orthostatic symptoms are minimized, perhaps indicating that this phenomenon is not solely related to posture. However, no studies have evaluated cognitive function in POTS during active standing. There are marked physiological differences between active standing and passive HUT. For example, during active standing the body engages the skeletal muscle pump to improve venous return to the heart. Furthermore, passive HUT can elicit exaggerated hemodynamic responses and vasovagal episodes even in health participants with no prior experience of clinical faints (false positives). Since active standing is more physiologically relevant in terms of daily life, it is critical to better understand how standing impacts cognitive function in POTS.

### **Joint Hypermobility in POTS**

The high prevalence of hEDS in POTS was first recognized by [name], et al. in 1999. He found that about 60% of patients with chronic fatigue syndrome and orthostatic intolerance had joint hypermobility but this study was only conducted in 12 subjects. One small study found that 29% of pediatric POTS patients have joint hypermobility. Larger, questionnaire based studies have estimated that 30-40% of POTS patients have been diagnosed with EDS. But because there are very few geneticists that specialize in EDS and most physicians who evaluate POTS patients do not evaluate for EDS. The true prevalence of hEDS in POTS has not been evaluated. Furthermore, HSD is a new diagnosis defined in 2017, and no study to date has attempted to determine the rate of HSD in POTS.

# 2.3 Study Rationale

POTS patients have impaired cognitive function that impacts their daily life including school and work performance.  hEDS and HSD contribute to functional disability and pain in POTS but are often undiagnosed because the prevalence is unknown and most POTS patients are not evaluated. The current study will determine the impact of standing on cognitive function in POTS and investigate the prevalence of hEDS and HSD in POTS. The findings from this study will provide the foundation to explore mechanisms of cognitive function in POTS and improve physician awareness of the importance of evaluating EDS in POTS patients. We will perform this study at the 2018 Dysautonomia Patient Conference in Nashville, TN June 22-24, 2018. Performing this study at the conference will provide a convenience sample in which we can examine cognitive function and hEDS and HSD prevalence in a larger and more diverse cohort of POTS participants than could be accomplished at our institution. The mechanisms underlying cognitive dysfunction in POTS will be investigated more thoroughly at our institution under a separate IRB protocol (study STUDY00009333: Cognition in Postural Tachycardia Syndrome-submission in progress).

# 3.0 Inclusion and Exclusion Criteria

### 3.1 Inclusion Criteria

- Postural Tachycardia Syndrome or healthy control
  - Previously diagnosed with POTS
- Age between 13-60 years
- Participants may be any race, ethnicity, sex, or gender
- Able and willing to provide informed consent

#### 3.2 Exclusion Criteria

- Inability to give, or withdrawal of, informed consent
- Age ≤ 13 or ≥ 61 years
- Prisoners
- Unable to stand
- Healthy controls must be free of chronic and systemic illness and not have a history of recurrent syncope

### 3.3 Early Withdrawal of Subjects

### 3.3.1 Criteria for removal from study

The subject may withdraw from the study at any time for any reason.

### 3.3.2 Follow-up for withdrawn subjects

No follow-up is required.

# 4.0 Recruitment Methods

We will conduct this study at the 2018 Dysautonomia International Patient conference if our proposal is selected for the conference by Dysautonomia International's Board of Directors. Healthy control subjects will be recruited using Penn State study finder and a paper flyer.

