### 8.2 Sample size determination

We propose to enroll up to 100 POTS patients and 50 healthy controls. We expect that this convenience sample, based on meeting attendance and recruitment feasibility, will allow for sufficient data on the prevalence of hEDS and HSD in POTS and whether cognition is affected by orthostasis in this patient population.

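### The unadjusted Mann-Whitney comparison of POTS patients with unmatched controls can mix POTS with age and sex; the within-person posture test is not affected

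*Combined protocol and SAP*

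**What the plan says.** Section 4.0 (repeated in 4.1) gives the control source: "Healthy control subjects will be recruited using Penn State study finder and a paper flyer". POTS patients are attendees at a three-day conference in Nashville. Section 3.1 sets one age range, 13-60 years, for both groups and adds "Participants may be any race, ethnicity, sex, or gender". The only rule specific to controls, in 3.2, concerns health status. No section mentions matching, quotas or stratification.

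Section 2.2 says of POTS that "it predominantly effects women of childbearing age". The background on cognition describes an earlier seated study in which patients were "compared to age-matched healthy participants".

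Section 1.2 makes cognitive scores a primary endpoint. Section 8.3 has two sentences: Wilcoxon signed-rank tests by position, and "Results will be compared between groups (POTS, controls) using Mann-Whitney U test". It names no covariate and does not say whether supine scores, standing scores or their difference are compared. On numbers, 8.2 says "We propose to enroll up to 100 POTS patients and 50 healthy controls", and 16.2 adds "We expect to recruit 5-10 healthy subjects per month". Controls are tested at Hershey (1.1, 16.1). Under 7.3 only POTS patients complete questionnaires.

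**The concern.** The protocol's own description makes an imbalance foreseeable. The POTS group should be mostly younger women, and nothing steers the control group toward that profile. Stroop and reaction-time scores may well vary with age across 13 to 60. The documents do not say so, but it is a reasonable premise, and the earlier seated study thought age worth matching on.

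If scores do depend on age, a difference in age mix shifts one group's distribution whether or not POTS affects cognition, and an unadjusted rank test cannot tell the two apart. If performance worsens with age, older controls would mask a POTS deficit and younger controls would produce an apparent one. Sex raises the same issue.

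At stake is the one analysis that uses the 50 controls: whether POTS patients differ from healthy people.

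**Working it through.** **Inputs from the documents.** 100 POTS patients and 50 controls (8.2); unadjusted Mann-Whitney (8.3); shared range 13-60, any sex (3.1); 5-10 controls a month (16.2). There is no planning figure to reproduce: 8.2 calls the numbers a convenience sample and gives no effect size, SD, significance level or power.

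**Assumed, because the documents give none of it.** Two-sided 5% level; single-posture scores compared; normal scores with SD 1; age SD 12 years in each group, without truncation at 13 and 60; score-age correlation r of 0.3 to 0.5; no true POTS effect; a gap in mean age of 0, 2, 5 or 10 years.

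**Step 1, shift due to age alone.** Shift = r × gap / 12, in SD units. For 10 years: 0.3 × 10/12 = 0.25 and 0.5 × 10/12 = 0.417.

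**Step 2, standard error.** √(1/100 + 1/50) = √0.03 = 0.173.

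**Step 3, chance of p < 0.05.** With the Mann-Whitney efficiency 3/π, put k = √(3/π) × shift / 0.173 = 0.977 × shift / 0.173. The rejection rate is about Φ(k − 1.96) + Φ(−k − 1.96). For a shift of 0.25, k = 1.41 and the rate is about 29%.

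| Gap in mean age | Shift (r = 0.3 to 0.5) | Formula | Simulation |
|---|---|---|---|
| 0 years | 0 | 5% | about 5% |
| 2 years | 0.05 to 0.083 | 6% to 8% | 6% to 8% |
| 5 years | 0.125 to 0.208 | 11% to 22% | 12% to 22% |
| 10 years | 0.25 to 0.417 | 29% to 65% | 28% to 64% |

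Simulations used 4,000 runs per setting; repeat runs differ by one to two percentage points.

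**Step 4, effect of adjustment.** In the same settings a rank test stratified on four age bands (13-17, 18-29, 30-44, 45-60) rejected in about 4% to 7% of studies. A linear model with age as a covariate, simulated for gaps of up to one age SD and r of 0.2 to 0.5, gave 4.3% to 5.9%.

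**Step 5, comparing the change.** Suppose each score is a stable personal level (including age, sex and setting) plus a posture effect plus error. Subtracting supine from standing cancels the stable level. What survives is any difference in the response to standing, or to practice, that itself depends on age, sex or setting.

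**Step 6, site.** 50/10 = 5 months and 50/5 = 10 months of control testing at Hershey, against three days for POTS in Nashville. Every POTS patient is at one site and every control at the other, so a site term would be identical to the group term. No model can separate them.

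**The case against.** The strongest reply is that the study's stated hypothesis is not exposed. Hypothesis 1 is that standing worsens cognition in POTS. It is tested by comparing each patient with themselves, in one setting, so age, sex and site cannot confound it. Aim 2 has no controls. No hypothesis about a POTS-control difference is stated. All of this stands, and it is why the point ranks below a must-fix. The between-group test still bears on a primary endpoint, and without comparable controls a posture effect in POTS cannot be shown to exceed the normal response to standing.

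A reader might infer that 8.3 compares raw scores. It does not say so. If changes are meant, stable offsets cancel and the rates in the table do not apply.

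A reader might also take 28% to 64% as the plan's error rate. It is the result for one assumed 10-year gap. The shared 13-60 limits restrain the gap without preventing it, and with no gap there is no inflation. The direction of any bias assumes a steady relation between age and score that the documents do not establish.

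Nor does the text support saying that a safeguard was dropped. Age matching belonged to another study, and this protocol never adopted it.

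**Conclusion.** The point holds for the POTS-versus-control comparison only. As written, that comparison can mix POTS with age and sex, and nothing in recruitment or analysis guards against it. The inflation runs from none to severe (about 5% up to 64%) depending on an age gap and a score-age correlation that are both assumed. Absence of matching and adjustment is certain from the text; the size is not.

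A reader might conclude that no group difference could ever be attributed to POTS, or that Aim 1 fails. The documents do not support that. The within-person test stands, and a between-group comparison of change is free of stable age, sex and site offsets. The narrower statement is right: because site coincides with group, differences in single-posture scores should not be attributed to POTS alone, even after adjustment for age and sex. This is a cheap improvement, below must-fix.

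**What to change.** - **Section 4.1:** once the conference cohort's age and sex distribution is known, frequency-match the controls to it on sex and broad age bands. Conference enrolment ends on 24 June and controls accrue over 5 to 10 months, so the order is feasible. Keep the matching cells few: four age bands by two sexes would leave 50/8, about six controls per cell, with male cells probably near empty.
- **Section 7.2:** record age and sex for every control. Controls skip the questionnaires, and no demographic item is listed for them.
- **Section 8.3:** replace the unadjusted test with a rank test stratified by age band, or a rank-based model adjusted for age and sex. Name the between-group test of the supine-to-standing change as the main comparison, with single-posture scores as supportive.
- **Site:** state as a limitation that site and group coincide. Common testers and standardised conditions would reduce the problem but not remove it. Healthy conference attendees are not a dependable remedy: 16.2 describes attendees as mainly patients and caregivers, and anyone tested there would be enrolled before the POTS distribution is known.

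The cost is recruitment quotas, two recorded items and a revised analysis sentence, with no extra subjects. Control recruitment may be slower, some responders would be declined, and filling any adolescent band requires parental permission and assent under 5.3.3.
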